UFH	Unfractionated Heparin
WAIS	Wechsler Adult Intelligence Scale

Clarification of terms used:

Day 1 swab: Day 1 swab is defined as the swab taken before starting study drug. This could be on the same day as starting study drug.

Index case: The initial SARS-CoV-2 infected person who reached out for enrolment into the study. In the analysis, the index case is not analysed separately from the other household members. The index case does play a role in the randomisation by determining one of the randomisation strata. Some of the covariates included in multivariate models are also determined at the index case level.

Household contact: A household contact is any household member other than the index case.

Household member: This is a synonym for study participant, and means index cases and household contacts combined. For most analyses, we will include household members, by their SARS-CoV-2 status on day 1.

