2.7 Study procedures

When a participant is confirmed to be SARS-CoV-2 positive all consenting household members are enrolled and randomised to the same treatment arm. All consenting household members 5 years of age and older will be given the same study treatment. Treatment is 10 days and follow up for primary outcome is 10 days. Follow up for some secondary outcomes are 28 days and outcomes related to long COVID is 6 and 12 months post randomisation.

Daily communication via SMS, online or phone will be conducted by a research team member who will be trained in standard operating procedures as per trial manual. Paediatric or adult swabs (Rhinomed) will be provided to all participants with detailed instructions for self-collection and storage until collected by a research team member. Health care provider collected PCR nasopharyngeal swabs will be collected from all participants prior to commencement of study medication and on day 3, 5 and 10 (+/- 1 day for all time points).

Phone call follow up at day 14 and 28 by a research team member will assess which participants became symptomatic after the initial treatment period and whether participants required hospitalisation during that time. Detailed medical information as to reasons for hospital admission will be sought to confirm if admission was related to COVID-19 infection or for alternative reasons. Research team members will be trained specifically in questions to ask according to trial manual, which will include an escalation process if a research team member believes that additional clinical care is required for the participant or family member.

Telemedicine follow up at day 180 +/- 10 days and day 365 +/- 10 days to ascertain any evidence of long COVID neurological symptoms.

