3.3. Definition of baseline

Baseline is defined as day 1 PCR and pre-Day 1 measures for other measures. Only measures taken prior to dispending study drug will be used as baseline measures.

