3.9. Baseline covariate set

A set of covariates which will be included in models for all primary and secondary outcomes (unless specified otherwise) are: stratification factors (time from positive test to randomisation (binary)) and whether the index case is a child < 5 years(binary), participant age (continuous), inhaled steroid use at baseline (binary), days since symptom onset for index case at randomisation (continuous), whether there are children in the household (binary) and household size (continuous). This is referred to as the baseline covariate set.

Some of these covariates are correlated with each other and may also have sparse data in some of the cells, which may lead to convergence problems with the models. If that is the case, we will exclude some of the baseline covariate set until we can get a model that converges. We will first exclude the sparsest variables, and secondly exclude the variables most correlated with other variables.

We will also repeat each analysis with a model including only the two stratification variables.

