The analysis will follow the intention to treat principle, but only some households will be eligible for this objective. A household will be eligible if there is at least one participant in the household who tested positive to SARS-CoV-2 by PCR on Day 1 and one participant who tested negative to SARS-CoV-2 by PCR on Day 1, using the health care provider collected swab. It does not matter whether it was the index case or another household member who tested positive. Households where all participants test positive or where all participants test negative will not be eligible for this analysis.

Treatment arms will be compared using generalised linear mixed models (GLM) with infection status as the binary outcome, adjusting for stratification factors (time from positive test to randomisation, whether the index case is a child < 5 years), participant age, inhaled steroid use at baseline, days since symptom onset at randomisation, whether there are children in the household and household size (referred to as the defined baseline covariate set, see Section 3.9), with household as random effect to take the clustering by household into account. Both relative and absolute differences in proportions will be reported with 95% confidence intervals.

Relative differences (risk ratios) between the treatment arms will be calculated using a Poisson regression with robust standard errors in Stata as follows:

xtpoisson outcome i.arm baseline_covariates, re vce(robust) irr

Absolute differences (risk difference) between the treatment arms will be calculated in Stata as follows using a mixed effects GLM with random intercepts: megIm outcome i.arm baseline_covariates || household:, family(bin) link(logit)

The margins statement will be used to compute the risk difference by subtracting the probability of the outcome in the control arm from the probability in the treatment arm margins i.arm, atmeans post lincom _b[1.arm] - _b[0.arm]

Both these models are fairly complicated models to fit and might not converge if sparse data is encountered, given all the baseline covariates included. If the models do not converge, the following strategies will be tried:

- Exclude some of the baseline covariates especially binary covariates, covariates with sparse categories, or covariates with little variability
- Or, fit the following simpler models

Relative differences (risk ratios) between the treatment arms will be calculated in Stata as follows using robust standard errors:

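### The primary model's covariate set omits the number of household members already PCR positive on Day 1, a pre-drug exposure measure the trial collects, at a modest cost in precision and chance balance

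*SAP*

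**What the plan says.** Section 3.9 of the SAP gives a closed list of baseline covariates. It starts with the time-to-randomisation stratum, continues with "whether the index case is a child < 5 years(binary), participant age (continuous), inhaled steroid use at baseline (binary"), and ends with "days since symptom onset for index case at randomisation (continuous), whether there are children in the household (binary) and household size (continuous"). Section 5.1 repeats this list for the primary model and handles clustering "with household as random effect to take the clustering by household into account. Both relative and absolute differences in proportions will be reported".

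The number of members positive on Day 1 appears in none of these places:
- the randomisation strata (Section 2.5)
- the sensitivity analyses (Section 5.2)
- the primary subgroups (Section 5.4)
- the household characteristics to be tabulated (Section 4.2)

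Day 1 status is described by arm only at participant level (Sections 4.1 and 4.2, Tables 1 and 3).

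The information itself is collected. Section 2.7 states: "Health care provider collected PCR nasopharyngeal swabs will be collected from all participants prior to commencement of study medication". The clarification of terms states: "Day 1 swab is defined as the swab taken before starting study drug". Section 3.3 makes it the baseline: "Baseline is defined as day 1 PCR and pre-Day 1 measures for other measures". Section 5.1 uses it to select households: "A household will be eligible if there is at least one participant in the household who tested positive to SARS-CoV-2 by PCR on Day 1", together with at least one who tested negative.

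**The concern.** Eligibility requires only one positive and one negative member. In a four-person household with everyone enrolled, the number positive on Day 1 can therefore be one, two or three. A negative member living with three infectious people plausibly faces a higher risk by day 10 than one living with a single case.

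Household size does not separate these situations. Days since symptom onset describes only the index case, while Section 5.1 accepts households whichever member was positive. The random effect gives an appropriate standard error, but it neither explains differences in exposure nor corrects an arm difference in them.

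Allocation is by household, so between-household variation is a main part of the error of the treatment comparison. Two things are at stake: the precision of the primary comparison, and whether a chance arm difference in exposure stays in the estimate.

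**Working it through.** **Inputs from the SAP (Section 2.6).** Attack rates 85% and 75%; ICC 0.2; two-sided alpha 0.05; power 80%; 3 contacts per household (alternative 2); 120 households per arm, 134 after 10% loss.

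**Inputs not in the SAP, assumed as ranges.** Share R of between-household variance explained by the count, 0.10 to 0.50; SD of the count, 0.5 to 0.9; 3 to 10 points of risk per extra positive member.

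**Step 1: reproduce the plan's figure.** Two proportions, pooled variance, no continuity correction: [1.96·√(2·0.80·0.20) + 0.8416·√(0.85·0.15 + 0.75·0.25)]² / 0.10² = 250 per arm.
- With m = 3, the design effect is 1 + 2·0.2 = 1.4, and 250·1.4/3 = 117 households per arm against 120 stated. Power at 120 is 81.1%. 120/0.9 rounds up to 134.
- With m = 2, 250·1.2/2 = 150; 150/0.9 rounds up to 167 per arm, or 334 in total, as stated.

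**Step 2: precision by formula.** The variance of a household mean is proportional to ICC + (1 − ICC)/m. If the count explains a share R of the between-household part, the design effect becomes 1 + (m − 1)·ICC − m·ICC·R, which is 1.4 − 0.6R for m = 3.

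| R | Design effect | Households per arm for 80% | Power at 120 per arm |
|---|---|---|---|
| 0 | 1.40 | 117 | 81.1% |
| 0.10 | 1.34 | 112 | 82.8% |
| 0.25 | 1.25 | 105 | 85.3% |
| 0.50 | 1.10 | 92 | 89.4% |

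This table is generous. It ignores what household size and the other planned covariates already explain. It also holds three negatives per household, whereas in a household of given size each extra positive leaves one fewer negative to analyse.

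**Step 3: precision by simulation, with household size already in the model.** 240 households of 2 to 6 members; 1,000 runs per setting; linear model with cluster-robust errors, a simplification of the SAP's models. The number of negatives falls as the count rises.

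| Log-odds per extra positive | Power without count | Power with count | Gain (points) |
|---|---|---|---|
| 0.3 | 82.6% | 83.2% | 0.6 |
| 0.6 | 80.6% | 82.7% | 2.1 |
| 1.0 | 78.2% | 81.8% | 3.6 |

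Monte Carlo error on each power is about 1 point, so the smallest gain cannot be told from none. Type I error without the count was 4.6% to 5.6%. Where the count mattered, the correlation between the estimate and the arm imbalance was 0.11 to 0.22 without adjustment and 0.06 or less with it.

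**Step 4: size of chance imbalance.** The SE of the arm difference in mean count is SD·√(2/120): 0.065 for SD 0.5 and 0.116 for SD 0.9. The shift in the risk difference at 1.96 SE is:
- low end: 1.96 · 0.065 · 3 points = 0.4 points
- high end: 1.96 · 0.116 · 10 points = 2.3 points

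Both figures take no credit for the part of the imbalance that household size would remove.

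**The case against.** The SAP contradicts nothing here. It prespecifies seven covariates, a household random effect and a strata-only model. Chance imbalance in an unadjusted factor is already reflected in the confidence interval, and imbalance accounts for only about 1% to 5% of the estimate's variance (0.11² to 0.22²). All of this stands, and it limits the point to efficiency and balance in the realised sample.

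A reader might infer three stronger things that the documents do not support:

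- **That the primary analysis is biased or its error rate wrong.** Randomisation by household and the clustering term protect both, and the simulated type I error agrees.
- **That the count is the household's baseline value of the outcome.** The outcome is new infection among people who are all negative at baseline. The positives are other people, outside the analysed population, so the count is an exposure measure. No conventional baseline-to-outcome correlation can be borrowed for it, nor the large power gain such a correlation would imply.
- **That the gain is as large as the variance formula suggests.** The upper rows of Step 2 need the count to explain a quarter to a half of between-household variance beyond the planned covariates. The SAP gives nothing to support that.

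Three practical objections also stand:

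- The count is constant at 1 in two-person households.
- It covers only members who enrol and are swabbed, and Section 2.3 requires only one besides the index case to consent.
- Section 3.8 can settle an inconclusive Day 1 swab from a later result, so a count built on that algorithm could carry post-randomisation information.

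Convergence is a fair worry, since Sections 3.9 and 5.1 both anticipate it. That is a reason to fix the count's place in the drop order, not to leave it out.

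**Conclusion.** The point holds as a modest, inexpensive improvement. The primary model omits a plausible prognostic exposure measure that is collected before drug and already decides eligibility, and neither household size nor the random effect replaces it.

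The cost is roughly 1 to 4 points of power once household size is in the model, and an uncorrected chance shift of about 0.4 to 2.3 points against a planned 10-point difference. Both ranges rest on assumed values for the spread of the count and its link to risk, which the SAP does not give. Validity of the primary test is not in question.

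**What to change.** Before unblinding:

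1. Add to the Section 3.9 set, for the primary outcome, the number of enrolled household members PCR positive on Day 1 (1 versus 2 or more), based on pre-drug swab results only.
2. State that this term and the two stratification factors are the last to be removed under the convergence rules. As written, those rules remove sparse, binary or correlated terms first and could take any of the three. The order among the other covariates need not change.
3. Tabulate the count by arm at household level with the other household characteristics in Section 4.2.
4. Keep the strata-only model as the existing sensitivity analysis.

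The cost is a few sentences in the SAP and one table row; the swabs are already taken. The downside is one more term, uninformative in two-person households, in a model that the SAP warns may not converge.

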4. DESCRIPTIVE STATISTICS

4.1. Recruitment and follow-up

We will summarise the number of households and participants enrolled. We will also detail how many index cases, household members, SARS-CoV-2 positive and negative household members were enrolled. We will also show how many households were enrolled and were eligible for the primary analysis. This will be summarised in a CONSORT flowchart.

4.2. Baseline characteristics

The following variables will be summarised at baseline by treatment arm. Categorical variables will be summarised as the number and percentage, and continuous variables as mean, standard deviation (SD) and range (minimum and maximum) or median and interquartile range (IQR) when continuous data is skewed.

Household information: Household size, number of children in household, household type, number of bathrooms, number of bedrooms, number of household members enrolled.

Index case information: Time of positive test collection, index case <5 years old, age, interpreter required, sex, COVID-19 vaccine history (number of doses received), had COVID-19 before (number of infections), COVID-19 symptoms present (yes/no and fever or chills, cough, shortness of breath, fatigue, muscle or body aches, headache, loss of taste or smell, sore throat, congestion or runny nose, nausea or vomiting, diarrhea), number of days with symptoms, nasal spray use

Household member information: Age, interpreter required, SARS-CoV-2 status at screening, sex, COVID-19 vaccine history (number of doses received), had COVID-19 before (number of infections), COVID-19 symptoms present (fever or chills, cough, shortness of breath, fatigue, muscle or body aches, headache, loss of taste or smell, sore throat, congestion or runny nose, nausea or vomiting, diarrhea)

Demographic data at baseline will be provided for the household, index case and household members. For household members, the demographics will be provided overall, as well as by SARS-CoV-2 status.

4.3. Protocol deviations

Protocol deviations will be listed.

4.4. Compliance

Participants will be asked about compliance and symptoms daily. Parents will act as a proxy for children <16 years old. They will be asked how many doses they have used in the previous day. We will provide the number of participants who took 0, 1, 2 or 3 doses per day for 10 days.

We will also calculate the percentage of prescribed study dose that was taken. Each participant should take 3 doses per day, 30 doses over the 10 days. Participants could start the study late on the first day, in which case one would expect them to only have used 1 or 2 doses, instead of 3. Starting late on the first day would also distort reporting of study compliance on Day 2, since we ask "how many doses of study drug have you taken in the last 24 hours". We do not have the time of day when the study was started and thus cannot determine how many doses a participant should have used on the first or second day. For this reason, we will exclude Days 1 and 2 from the calculation of compliance. Thus, the percentage compliance will be calculated as (number of doses taken from days 3 to 10/24) multiplied by 100. If compliance data is missing for a day, the denominator will be reduced by 3. The mean percentage compliance will be summarised. All compliance summaries will be provided in each treatment arm as well as for participants who were positive and negative for COVID-19 at baseline by treatment arm.

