2.3 Study population

Adults or children in community setting with RAT or PCR-confirmed SARS-CoV-2 infection and their household contacts. All participants who enter the trial based on a positive RAT will have a confirmatory PCR test taken prior to commencing study medication. This is referred to as the Day 1 swab. Only participants who test PCR negative to SARS-CoV-2 on day 1 swab contribute to the primary outcome measure in addition to relevant secondary aims. Anyone testing PCR positive on day 1 contributes to relevant secondary aims only.

A household contact is defined as anyone living in the same house (street address) regardless of their direct biological relationships.

Children (<5 year old) in households are not treated but monitored only. For households in which the child is the index case, only household contacts >5 years age are randomised to treatment. For households in which the index case is an adult, and the child <5 years old tests PCR negative on day 1, then the child contribute to primary and secondary outcomes even though they themselves are not treated.

Inclusion criteria:

- Any person > 5 years of age who tests positive to SARS-CoV-2 or is a household contact of someone of any age who tests positive is eligible for the trial.
- Index case must be within 72 hours of positive test.
- The positive test can be a RAT or a standard PCR nasal swab performed at a National Association of Testing Authorities (Australia) (NATA) accredited laboratory for the diagnosis of COVID-19 as per the department of health regulations. If initial test is a RAT, then a standard PCR nasal swab performed at a NATA accredited laboratory for the diagnosis of COVID-19 as per the department of health regulations will be collected prior to commencement of study medication but does not delay entry into the study awaiting the confirmatory result.
- All participants must provide a signed and dated consent form and for children < 16 years have a legally acceptable representative capable of understanding the informed consent document and providing consent on the participant's behalf. Consent forms will be developed in multiple languages and provided in a language that the participants are fluent in speaking.

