5.3. Supplementary analyses

We define a supplementary estimand, through handing the intercurrent event of not taking study drug differently.

Supplementary estimand

Population: Household contacts who test negative for SARS CoV-2 on day 1 (baseline) PCR testing using the health care provider swabs

Treatment: Unfractionated intranasal heparin 1400u each nostril (as heparin solution 5,000u/ml, 140microL/actuation, TWO actuations each nostril) THREE times daily via a plastic nasal inhalator device or saline control

Outcome: Testing positive for SARS-CoV-2 by PCR on any of three health care provider collected swabs at days 3, 5 and 10 while participant and index case do not discontinue treatment due to adverse events. The algorithm to determine SARS-CoV-2 positivity is described in detail in Section 3.8. If one of the post-baseline swabs is missing, but all observed swabs were negative, the participant will be regarded to be negative. If more than one post-baseline swab is missing and the observed swabs were all negative, the outcome will be regarded to be missing.

Summary measure: Both relative (risk ratio) and absolute differences (risk difference) in proportions will be reported with 95% confidence intervals

Potential intercurrent events:

Index case in the household not taking study drug. This is defined as compliance <90% Participant (this household member) not taking study drug. This is defined as compliance <90% Either participant (this household member) or index case stop treatment due to adverse event Participant hospitalisation during first 10 days (removed from household) Participant received an anti-viral

Strategy for handling intercurrent event:

Index case in the household not taking study drug. This is defined as compliance <90%: This intercurrent event will be handled following the hypothetical strategy. For index cases who used <90% of study drugs we will set all SARS-CoV2 infections observed in the household to missing. We will use multiple imputation to impute these outcomes.

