Participant (this household member) not taking study drug. This is defined as compliance <90%: This intercurrent event will be handled following the hypothetical strategy. We will set all SARS-CoV2 infections observed to missing. We will use multiple imputation to impute these outcomes. Either participant (this household member) or index case stop treatment due to adverse event: We will handle this intercurrent event using the while on treatment strategy. We will do this by excluding outcomes after participants stop study treatment due to adverse events from the analysis. All other intercurrent events will be handled by using the treatment policy strategy, which means that those intercurrent events will be ignored.

This analysis will only be done if more than 7% of participants had the intercurrent events.

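### Compliance is scored on reported days only, with no minimum, so a participant who stops both drug and diary can escape the below-90% rule in the supplementary analysis

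*SAP*

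**What the plan says.** SAP Section 4.4 starts from a full course: "Each participant should take 3 doses per day, 30 doses over the 10 days". Because the time of the first dose is not recorded, "we will exclude Days 1 and 2 from the calculation of compliance", and "the percentage compliance will be calculated as (number of doses taken from days 3 to 10/24) multiplied by 100". Gaps in the diary are then handled in one sentence: "If compliance data is missing for a day, the denominator will be reduced by 3". The section gives no minimum number of reported days and no rule for a participant with none.

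Section 5.3 turns this score into two intercurrent events: "Index case in the household not taking study drug. This is defined as compliance <90" per cent, and "Participant (this household member) not taking study drug. This is defined as compliance <90" per cent. Both are handled by a hypothetical strategy. The infections concerned (the whole household's, if the index case is flagged) are set to missing and multiply imputed. Stopping because of an adverse event is a separate event with a while-on-treatment strategy. The section ends with a trigger: "This analysis will only be done if more than 7% of participants had the intercurrent events". Section 6.1 repeats the supplementary analysis for measures 1.1 to 1.3.

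On young children, Section 2.3 says: "Children (<5 year old) in households are not treated but monitored only". Neither Section 4.4 nor Section 5.3 says what their compliance value is.

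**The concern.** Taking unreported days out of the denominator assumes that the dose rate on silent days equals the rate on reported days. That is least safe where it matters most, because a participant who loses interest may well stop spraying and stop answering together. Such a person keeps the high score earned earlier and is treated as having taken the drug, whereas an equally non-adherent but conscientious reporter is flagged. The flag decides whose outcomes are replaced by imputed values and feeds the decision whether to run the supplementary analysis at all. A classification that turns on reporting behaviour rather than on drug use weakens an estimand meant to describe what would happen had the drug been taken.

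A smaller gap sits beside it. Children under 5 get no drug but can be contacts or index cases, and the below-90% events are written without an exemption for them.

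**Working it through.** **Inputs (SAP Sections 4.4 and 5.3).** Three doses a day; days 3 to 10 counted (8 days); denominator cut by 3 for each unreported day; threshold 90%.

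**The plan's own figures.** 10 × 3 = 30 doses over the course and 8 × 3 = 24 over days 3 to 10. Both reproduce.

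**Score with k reported days.** The denominator is 24 − 3(8 − k) = 3k. If all three doses were taken on each reported day, the score is 3k/3k = 100% for any k from 1 to 8. If the silent days were in fact undosed, the share of the 24 doses actually taken is 3k/24. The last column shows the score under the SAP rule when exactly one dose was missed on the reported days, (3k − 1)/3k.

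| Reported days k | Last report if consecutive | SAP score, fully dosed | Lower bound, silent days undosed | SAP score, one dose missed |
|---|---|---|---|---|
| 0 | none from day 3 | 0/0, undefined | 0% | undefined |
| 1 | day 3 | 3/3 = 100% | 3/24 = 12.5% | 2/3 = 66.7% |
| 2 | day 4 | 6/6 = 100% | 6/24 = 25% | 5/6 = 83.3% |
| 3 | day 5 | 9/9 = 100% | 9/24 = 37.5% | 8/9 = 88.9% |
| 4 | day 6 | 12/12 = 100% | 12/24 = 50% | 11/12 = 91.7% |
| 5 | day 7 | 15/15 = 100% | 15/24 = 62.5% | 14/15 = 93.3% |
| 6 | day 8 | 18/18 = 100% | 18/24 = 75% | 17/18 = 94.4% |
| 7 | day 9 | 21/21 = 100% | 21/24 = 87.5% | 20/21 = 95.2% |
| 8 | day 10 | 24/24 = 100% | 24/24 = 100% | 23/24 = 95.8% |

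**Same drug use, two classifications.** Two participants take three doses on each of days 3 and 4 and none afterwards. One goes silent: 6/6 = 100%, not flagged. The other reports zeros on days 5 to 10: 6/24 = 25%, flagged.

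**The error can run the other way.** One missed dose flags a participant with one, two or three reported days (66.7%, 83.3%, 88.9%) but not one with all eight (95.8%).

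**Children under 5.** Recorded as zero doses, the score is 0/24 = 0%, below 90%. Not recorded, it is 0/0. Read as a share of a prescribed dose, it does not apply, since none is prescribed. Section 5.3 does not choose among these. The choice matters for a contact under 5, because the supplementary population is day-1-negative contacts with no age limit. It also matters for an index case under 5, which is a randomisation stratum in Section 2.5.

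**The case against.** Scoring on available days is a common convention, and much of the danger is reduced elsewhere. Section 2.7 has staff in daily contact with participants, so a zero dose count that is reported keeps its place in the denominator. Discontinuation before day 10 is captured separately as measure 2.1. Adverse-event stops have their own strategy and do not depend on the 90% score. A contact who leaves follow-up after day 4 will usually miss the day 5 and day 10 swabs; if the day 3 swab was negative, that person's outcome is already missing under Section 5.3.

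All of this stands, and it narrows the problem to participants who keep being swabbed but stop reporting, and to silent index cases, whose score governs the rest of the household. It does not remove it. Section 4.4 makes no use of a recorded discontinuation, and the adverse-event rule does not cover stops for other reasons.

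Three stronger readings are tempting and are not supported:

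- A reader might infer that anyone who stops reporting is scored fully compliant. That is not so: two doses on day 3 and then silence gives 2/3 = 66.7%, and silence from day 3 is undefined. The 100% arises only when every reported day was fully dosed.
- A reader might take the 25% as that participant's true compliance. It is a lower bound that assumes undosed silent days; the truth lies between 25% and 100%.
- A reader might infer that every household with an index case under 5 is discarded from the supplementary analysis. Section 4.4 speaks of the prescribed dose, and Section 3.4 limits those prescribed drug to age 5 and over, so the natural reading is that compliance does not apply. What is missing is a sentence saying so.

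**Conclusion.** The concern holds in a limited form. As written, the compliance score is the dose rate on reported days, with no floor on how many days that is. A fully dosed participant who stops drug and diary together therefore escapes the below-90% event, while an identical user who reports zeros does not. For one to seven reported days the gap between the SAP score and the lower bound runs from 87.5 down to 12.5 percentage points, and every lower bound falls below 90%.

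The reach is the supplementary estimand, its repeat for measures 1.1 to 1.3, the 7% trigger and the compliance summaries. The primary analysis ignores these events under the treatment policy strategy and is untouched. The number of participants misclassified cannot be computed, because the SAP gives no reporting rates and no count of children under 5. Nor can the net effect on the 7% count be signed: silent stoppers lower it, whereas children scored at 0% would raise it. It would go too far to say that the supplementary estimand is defeated. This is an improvement worth making, not a threat to the trial's main conclusion.

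**What to change.** Amend Sections 4.4 and 5.3 as follows.

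1. Count each day after a recorded treatment discontinuation as zero doses, with the denominator kept at 24. Leave adverse-event stops under their existing while-on-treatment strategy, so that they are not also caught by the 90% rule. This assumes that the date of stopping is held alongside the fact of stopping needed for measure 2.1.
2. Where no stop is recorded and fewer than a pre-stated number of the eight days are reported (for example six), treat compliance as unknown. This covers the 0/0 case. Run the supplementary analysis twice, once with these people flagged and once without, and state which count feeds the 7% trigger. The cut-off is a judgement: at six reported days, full dosing still leaves a range of 75% to 100%.
3. State that both compliance events and the 7% count apply only to people prescribed study drug. They then do not apply to an untreated child under 5, including an index case under 5.

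The cost is a few sentences, one additional run of a conditional analysis, and a mean compliance figure that may look slightly lower. No new data are needed if stop dates are recorded.
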